8.2. Adverse Events of Special Interest Analyses

Cardiovascular (CV) AEs, gastrointestinal (GI) AEs, *C. difficile* AEs, and AEs related to Acetylcholinesterase Inhibition (AChE-I) as determined by algorithm will be considered AESIs.

8.2.1. *Clostridium difficile* AESI

C. difficile AESIs (PTs *Clostridium difficile* infection and *Clostridium difficile* colitis) will be included in the overall summary of AEs. *C. difficile* laboratory testing results are collected and recorded on distinct eCRF pages, which will be presented in a separate subject listing.

8.2.2. Cardiovascular and Gastrointestinal Adverse Events

Gastrointestinal AESIs are defined as AEs with a gastrointestinal SOC. Cardiovascular AESIs are defined as AEs with PTs that match the terms listed in Appendix 4 (Section 12.4.3).

For cardiovascular and gastrointestinal AESIs, the number and percentage of participants with an event will be summarized by PT and the maximum grade. In addition, the incidence of AEs of gastrointestinal effects and time to the first occurrence will be summarized. Graphical presentation of the cumulative distribution of time to the first gastrointestinal event occurrence will be provided via Kaplan-Meier curve (participants with no occurrence will be regarded as censored at the last day of the study). The details of data displays are presented in Appendix 9.

8.2.3. Acetylcholinesterase-Inhibition Adverse Events

Any reported AE listed in the table in Section 12.4.3 with a start time no later than 12 hours after the last dose administered, as evaluated by the investigator as per the DMID grading criteria provided in in protocol Section 12.5 and Appendix 7, will be included in the programmatic identification of AChE-I related AESI. The list of preferred terms for

programming to be considered due to potential AChE-I is provided in Appendix 4 (Section 12.4.3).

Cumulative grade score of Acetylcholinesterase-Inhibition (AChE-I) will be calculated as the sum of the grade of each reported AE. This enables the number of AEs and the severity of each AE to be considered. The grading scale is defined as

Cumulative Grade:	0	1	2	3	4
Cumulative Grade Score:	0	1 to 3	4 to 6	7 to 10	>=11

For instance, if a participant reports two AEs, one of Grade 1 and the other of Grade 3 their cumulative grade score of 4 would result in cumulative grade 2. This will be calculated for All AChE-I events, non-GI AChE-I events and GI AChE-I events.

Acetylcholinesterase inhibition AESIs will be listed and tabulated by SOC and preferred term and maximum grade. Non-GI AChE-I events will also be summarized. A separate table will summarize the AChE-I AESI by the number of events and unique preferred terms. In addition, time of onset (time from first dose to the onset of first event in hours), duration, and lag time (the time from last dose to the end date/time of the last event for subjects whose end date/time of the last event is after treatment end date/time) of AChE-I event will also be summarized and repeated for non-GI AChE-I and GI AChE-I events. AChE-I events with a start time less than 6 hours after the latest dose administered will also be flagged in listings.

Graphical presentation via stacked bar charts of percentage of subjects in each AChE-I cumulative grade will be produced for All AChE-I events and non-GI AChE-I events separately. In addition, a forest plot of relative risk of AChE-I events between two treatment groups and its 95% Wald CI for each event will also be included. The details of the planned displays are provided in Appendix 9.

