2.3. Study Design

Overview of Study Design and Key Features	
Design Features	
 Phase III, randomized, multicenter, open-label (sponsor-blinded), comparator-controlled, noninferiority study The study duration is approximately 21 days with 3 planned study visits: 
 Baseline (Day 1) Visit TOC (Day 4 to 8) Visit Follow-up (Day 14 to 21) Visit The study will screen and randomize approximately 620 participants to obtain approximately 400 participants with culture-confirmed urogenital gonorrhea in the Micro-ITT Population, for an estimated total of 200 participants per treatment group in the Micro-ITT Population. Enrollment will continue until the target number of participants in the Micro-ITT Population has been reached.
Dosing	
 Participants will receive 1 of the following study treatments: 
 Gepotidacin: 3000 mg administered orally at the study site during the Baseline (Day 1) Visit followed by self-administration of a second oral 3000-mg dose as an outpatient 10 to 12 hours after the first dose. Ceftriaxone plus azithromycin: A single IM 500-mg dose of ceftriaxone plus a single oral 1-g dose of azithromycin administered at the study site during the Baseline (Day 1) Visit.
Time & Events	
 Refer to Appendix 1: Schedule of Activities
Treatment Assignment	
 Participants will be stratified by sex and sexual orientation (men who have sex with men [MSM], men who have sex with women [MSW], or female) and age (<18 years, ≥18 to 65 years, or >65 years). The MSM category will include MSM and bisexual males (i.e., male participants who have sex with both males and females) and participants ≥12 years will be included in the study. Eligible participants will be randomly assigned in a 1:1 ratio to receive 1 of the study treatments (gepotidacin or ceftriaxone plus azithromycin) with dosing as described above.
Interim Analysis	
 No interim analyses are planned for this study.

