8.1. Adverse Events Analyses

All AEs will be collected from the start of treatment until the FU visit and all SAEs will be collected from the signing of the informed consent form until the FU visit based on the timepoints specified in Appendix 1. All reported AEs will be coded using Medical Dictionary for Regulatory Activities (MedDRA) and summarized by system organ class (SOC) and preferred term (PT).

A treatment emergent AE (TEAE) is defined as an AE with start date/time after the first dose date/time of the study treatment. If the time part is missing, only dates will be considered. The number and percentage of TEAEs, study treatment-related AEs, non-serious drug-related AEs, SAEs, and AEs leading to study treatment or study withdrawal will be provided. Any AE starting before the first dose date/time will not be included in any summary analyses but will be displayed in the listings. Therefore, only TEAEs will be included in summary tables with all AEs displayed in listings.

The severity of AEs and SAEs will be determined by the investigator according to the US National Institute of Allergy and Infectious Diseases Division of Microbiology and Infectious Diseases (DMID) criteria for adult toxicity assessment, except for serum creatinine adolescent laboratory data, which will be assessed using DMID pediatric toxicity criteria. Adverse event severity is classified as mild (Grade 1), moderate (Grade 2), severe (Grade 3), potentially life-threatening (Grade 4), or resulting in death (Grade 5). Adverse events starting after the first dose of study treatment with a missing severity will be classified as severe. If a participant reports an AE more than once within the same SOC/PT, the AE with the worst-case severity will be used in the corresponding severity summaries.

The relationship to study treatment, as indicated by the investigator, is classified as “not related” or “related”. Adverse events with a missing relationship to study treatment will be regarded as “related” to study treatment. If a participant reports the same AE more than once within an SOC/PT, the AE with the worst-case relationship to study treatment will be used in the corresponding relationship summaries.

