10. BENEFIT/RISK

Forest plots showing the treatment effect and confidence intervals related to benefits and risks of treatment with gepotidacin will be created. Benefits will be represented by risk differences and corresponding confidence intervals from the following analyses based on the Micro-ITT analysis population:

- Microbiological outcome and response rate of urogenital Gonorrhea at the TOC Visit (primary analysis),
- NAAT outcome and response rate of urogenital Gonorrhea at the TOC Visit (exploratory analysis).

For these analyses, risk differences and 95% confidence intervals will be determined using the methods described in Section 7.1.6.1 and Section 7.3.1.5, respectively. Additionally, relative risks and corresponding 95% confidence intervals will be displayed for the following safety endpoints: incidence of AEs, SAEs and, separately, CV, GI, *C. difficile*, and AChE-I AESIs using the Safety analysis population. Confidence intervals for relative risks will be determined using the asymptotic Wald method.

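### Acetylcholinesterase-inhibition events are counted to 12 hours after the last dose, so the planned relative risks compare 22–24 hours on gepotidacin with 12 hours on the comparator

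*SAP*

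**What the plan says.** SAP 8.2.3 sets one rule for both arms: a reported event on the preferred-term list qualifies if it occurs "with a start time no later than 12 hours after the last dose administered". The summaries start at first dose, because under SAP 8.1 "only TEAEs will be included in summary tables with all AEs displayed in listings".

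SAP 2.3 describes gepotidacin as a first dose at the site followed by "self-administration of a second oral 3000-mg dose as an outpatient 10 to 12 hours after the first dose". The comparator is "A single IM 500-mg dose of ceftriaxone plus a single oral 1-g dose of azithromycin administered at the study site", so its first dose is also its last.

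The counts go into between-arm estimates. SAP 8.2.3 states that "a forest plot of relative risk of AChE-I events between two treatment groups and its 95% Wald CI for each event will also be included" (Figure 3.106), and Table 3.107 gives AChE-I frequencies with relative risks. SAP 10 says that "relative risks and corresponding 95% confidence intervals will be displayed for the following safety endpoints", and AChE-I events are one of those endpoints (Figure 3.301). The same counts feed Tables 3.118–3.120 and the cumulative-grade bars in Figures 3.103 and 3.104.

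Neither document specifies a common window, an adjustment for observation time or an equal-window sensitivity analysis for these events. The 6-hour flag in SAP 8.2.3 goes to listings only.

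**The concern.** A relative risk is read as a contrast between treatments. Here the comparator supplies the background rate, and that background is observed for about half as long. The background is unlikely to be nil. The list in SAP 12.4.3 includes nausea, vomiting, diarrhoea, flatulence and abdominal pain, and protocol 3.3.1 expects diarrhoea or loose stools with both ceftriaxone and azithromycin.

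Any such event starting more than 12 hours after the first dose is dropped in the comparator arm, but counted in the gepotidacin arm if it starts by 22–24 hours. Because the cumulative score in SAP 8.2.3 adds grades over events, a longer window can also raise that score. The AChE-I estimates, including the AChE-I row of the benefit/risk plot, would then look worse for gepotidacin than a like-for-like comparison would show.

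**Working it through.** **Plan's own figure.** SAP 8.5.2 bases a 90% chance of seeing at least one event on 310 gepotidacin participants and a true incidence of 0.75%: 1 − (1 − 0.0075)^310 = 0.903, which agrees. I take 310 per arm below, since "Eligible participants will be randomly assigned in a 1:1 ratio" and about 620 are randomized. The SAP states no per-arm window length and no expected AChE-I relative risk.

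**Window from first dose.**
- Gepotidacin, both doses on schedule: 10 + 12 = 22 h to 12 + 12 = 24 h.
- Comparator: 0 + 12 = 12 h.
- Ratio: 22/12 = 1.83 to 24/12 = 2.00.
- Gepotidacin participant who misses the second dose: 12 h.

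**Expected relative risk with no difference between arms.** Give both arms the same event process from first dose, with cumulative hazard H(t). Then RR = [1 − exp(−H(T))] / [1 − exp(−H(12))], with T = 22 or 24. The 12-hour background risk p is not in the documents, so it is assumed.

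*Constant hazard:* h = −ln(1 − p)/12. For p = 2%, h = 0.00168 per hour. At T = 22 the risk is 0.0364 and RR = 1.82; at T = 24 the risk is 0.0396 and RR = 1.98. The last column is the chance, by exact binomial enumeration at 310 per arm, that the lower 95% Wald limit exceeds 1. Outcomes with a zero cell count as not exceeding 1.

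| Assumed 12 h risk | Null RR, T = 22 to 24 | Chance lower limit > 1 |
|---|---|---|
| 1% | 1.83 to 1.99 | 5% to 7% |
| 2% | 1.82 to 1.98 | 19% to 26% |
| 5% | 1.80 to 1.95 | 49% to 62% |
| 10% | 1.76 to 1.90 | 78% to 89% |

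*Hazard decaying from first dose:* H(t) = c(1 − exp(−kt)), with k = ln 2/half-life and c = −ln(1 − p)/(1 − exp(−12k)). For p = 2%, half-life 6 h and T = 24: c = 0.0202/0.75 = 0.0269, H = 0.0269 × 0.9375 = 0.0253, risk 0.0249, RR = 1.25. Ranges below cover T = 22 and 24 and p = 2% and 10%.

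| Hazard half-life | Null RR |
|---|---|
| 2 h | about 1.02 |
| 3 h | about 1.06 |
| 6 h | 1.21 to 1.25 |
| 12 h | 1.41 to 1.49 |
| 24 h | 1.56 to 1.70 |

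**Missing start times.** SAP 12.5.2.1 sets a missing start time to midnight of the start date. For a first dose at clock hour t, an untimed Day 2 event falls 24 − t hours after it. A comparator participant has it counted only if 24 − t ≤ 12, that is, if dosed at noon or later. For gepotidacin the condition is 24 − (t + 10 to 12) ≤ 12, which any daytime first dose meets. The convention therefore acts differently by arm.

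**With one common window.** The null RR is 1.00 by construction. At 310 per arm the chance that the lower limit exceeds 1 is 1.3%, 2.2% and 2.4% for a risk within the window of 2%, 5% and 10%.

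**The case against.** The 12-hour anchor has a rationale. Protocol 3.3.1 describes the inhibition as rapidly reversible, and protocol Appendix 10 treats diarrhoea during or within 12 hours after dosing as suggestive of a cholinergic effect. Events caused by the second dose are real effects of the regimen and belong in the gepotidacin count. This supports attributing an event to a dose. It does not equalise the time over which background events are counted, and only those events create the bias.

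A reader might infer that relative risks are inflated 1.8- to 2-fold. The documents do not support that: it is the constant-hazard end of the range. A steady 2%, 4% or 8% per 12 hours would give about 57%, 82% or 97% of participants an event within 21 days (1 − (1 − p)^42), so the higher rates are more plausible as clustering after dosing, where the inflation is smaller.

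A reader might also infer that the distortion cannot be undone. Adverse events are collected in both arms to Follow-up and start times are used, so an equal-window count can be derived later; it is simply not prespecified. Equal-follow-up comparisons are already planned: common-event relative risks (SAP 8.1, Table 3.106), and gastrointestinal events with no 12-hour limit and a time-to-first-event curve (SAP 8.2.2). These overlap with the AChE-I terms and give a partial cross-check, not a correction.

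Two neighbouring matters are not part of this point. Figure 3.105 is a gastrointestinal display. How single grades map to the cumulative grade is unrelated to window length, and maximum grade is tabulated anyway.

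**Conclusion.** The imbalance is real and follows directly from the text: 22–24 hours against 12 for participants dosed on schedule. It raises the AChE-I relative risk, against gepotidacin. With no true difference the expected value lies between about 1.0 and 1.8–2.0, depending on how quickly events fall off after the first dose. The documents give neither that shape nor the background rate. The inflation vanishes only if no background events start after hour 12.

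The reach is limited to the AChE-I displays. The primary efficacy conclusion is untouched. The adverse-reaction short list is not affected either, because SAP 8.5.2 adds events of special interest automatically and bases its relative risks by high-level term on all treatment-emergent events. In the benefit/risk plot only the AChE-I row is affected. It would go too far to conclude that the overall safety comparison is unreliable.

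**What to change.** For the between-arm AChE-I displays (Tables 3.107 and 3.118–3.120, Figures 3.103, 3.104 and 3.106, and the AChE-I row of Figure 3.301), count events from first dose to 24 hours after first dose in both arms. This contains the whole gepotidacin window when the second dose is on schedule.

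Apply the midnight convention for missing start times relative to first dose in these displays. Midnight at the start of Day 2 is then always within 24 hours of a Day 1 dose, and midnight at the start of Day 3 always beyond it, so the rule treats both arms alike.

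Keep the 12-hour last-dose window for listings and for describing onset, duration and lag.

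The cost is SAP wording and one derived flag. Some later background events in the comparator arm will be counted. Events following a second dose taken more than 12 hours after the first may fall outside the common window, but they stay in the dose-anchored listing.

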3.3.1. Risk Assessment

Potential Risk of Clinical Significance	Summary of Data/Rationale for Risk	Mitigation Strategy
Gepotidacin (GSK2140944)		

Cardiovascular Effects
 
Based on nonclinical data, cardiovascular effects were reversible increase in heart rate and blood pressure (dog and monkey); reversible 10 to 21 msec (4% to 9%) increase in QTc (monkey); and at the highest dose, a reversible 2 to 3 msec (6% to 8%) increase in QRS (monkey).
 
Based on a thorough QTc clinical study, gepotidacin may cause mild, reversible heart rate effects and QT prolongation.
	
In a thorough QTc study, infusion of gepotidacin at doses of 1000 and 1800 mg over 2 hours caused a mild increased heart rate effect of approximately 6 to 10 bpm and QT prolongation measured as $\Delta\Delta\text{QTcF}$ of 12 to 22 msec. The QT prolongation evolved during the infusion and was quickly reversed over 2 hours after the end of the infusion (see Section 5.2.6 and Section 6 of the IB).
 
In Phase I and II studies, concentration-dependent QT prolongation has been observed during clinical trials with gepotidacin; however, this increase has not translated into medically significant QTc values or changes from baseline ($\text{QTcF} > 500$ msec or change from baseline > 60 msec) or cardiovascular safety concerns.
 
In Phase I and II studies, gepotidacin did not have a clinically relevant effect on cardiac conduction (PR and QRS intervals).
	
See Section 6.2 for excluded cardiac conditions. Close monitoring of clinical parameters and AEs (Section 2, Table 1) will be conducted, and treatment monitoring and evaluation criteria (Section 8.1.2) will be utilized to mitigate cardiovascular effects.
 
Participants taking medications known to increase QT or potent CYP3A4 inhibitors will be excluded (Section 7.7.2).
 
See also the Hepatic and Renal sections within this table below.

Potential Risk of Clinical Significance	Summary of Data/Rationale for Risk	Mitigation Strategy

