
Acetylcholinesterase Inhibition
 
In vitro testing showed gepotidacin to be a rapidly reversible inhibitor of acetylcholinesterase in the clinical plasma concentration range.
 
Based on clinical data, caution should be used in participants who have a condition requiring treatment with anticholinergic medications or who have certain medical conditions that may be exacerbated by the acetylcholinesterase inhibition activity of gepotidacin.
	
Increased cholinergic effects can potentially be associated with more severe symptoms including atrioventricular block, seizure/convulsions, bronchospasm, and vasovagal syncope. No causal relationship between these events and the use of gepotidacin has been established during clinical trials to date.
 
Adverse events possibly consistent with acetylcholinesterase inhibition, including diarrhea, nausea, vomiting, gastrointestinal cramping and pain, dyspnea, bradycardia, lacrimation, salivation, dysarthria, and diaphoresis/sweating have been reported during clinical trials with gepotidacin.
 
The majority of these AEs have been mild and transient and have been reported in clinical trials with comparable C_{max} levels expected in this study.
	
Participants who have medical conditions or require medications that may be impacted by inhibition of acetylcholinesterase will be excluded from participation in this study. See Section 6.2, for excluded medical conditions and Section 7.7.2, Prohibited Medications and Nondrug Therapies, for prohibited medications.
 
Close monitoring of clinical parameters and AEs will be conducted to assess effects potentially related to acetylcholinesterase inhibition (Section 2, Table 1).

Potential Risk of Clinical Significance	Summary of Data/Rationale for Risk	Mitigation Strategy

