9.2.5. Adverse Events of Special Interest

Predefined AEs of special interest for this study are cardiovascular (CV) events, gastrointestinal events, *C. difficile* infection or colitis events, and AEs related to acetylcholinesterase inhibition (see Section 3.3.1), which will be identified by a prespecified list of coded terms or determined by algorithm, as described in the reporting and analysis plan (RAP). Additional details are provided in Appendix 4.

C. difficile specimens were analyzed at IHMA, Inc. Addresses for the central laboratories, as well as all local laboratories, are provided in the List of Clinical Laboratories Used for Human Biological Sample Analysis, which will be stored in the trial master file.

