The incidence of treatment emergent AEs at HLT level for each treatment group with relative risk (95% CI) will also be presented graphically. In addition to potential ARs identified using the screening criteria shown above, AESIs (specified in Section 8.2 will be automatically included in the “short list” of potential ARs.

ARs listed in the Development Core Safety Information (DCSI) for gepotidacin will be re-assessed using data from this study to determine whether they should be carried forward as ARs based on the current supporting data.

Extra care has been taken when considering labelled/known ARs, such as fungal infections and hepatobiliary disorders, for the active comparators, ceftriaxone and azithromycin. It is not known whether the investigational product, gepotidacin, may also cause the event known to be associated with the active comparator, and therefore quantitative criteria may not be met if the incidence of these ARs are similar for the investigational product, gepotidacin.

The following AEs will automatically be included in the “short list” of potential ARs for further qualitative evaluation:

- QT Prolongation: It is a very rare serious event that has been observed in early phase gepotidacin studies and therefore needs further evaluation. It is identified using HLT “ECG investigations”.
- Serious and severe adverse events: The incidence of serious and severe AEs is expected to be very low, and the qualitative assessment will be applied directly to these events without going through the quantitative screening process.
- Fungal infections: It is a known AR for ceftriaxone plus azithromycin. It is identified using HLT “Fungal infections”.
- Hepatobiliary disorders: It is a known AR for ceftriaxone plus azithromycin. It is identified using HLT “Hepatic and hepatobiliary disorders”.

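### The AChE-inhibition AESI term list omits dysarthria and AV block, both named in Protocol 3.3.1, and the SAP does not describe the manual review that could catch them

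*SAP*

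**What the plan says.** Protocol 9.2.5 makes AEs related to AChE inhibition an AESI category, pointing to Section 3.3.1. The AESIs are events "which will be identified by a prespecified list of coded terms or determined by algorithm", with details left to the analysis plan.

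Under AChE inhibition, Protocol 3.3.1 gives two groups of events. The first may fit AChE inhibition and has been seen with gepotidacin: it covers gastrointestinal symptoms, dyspnea and bradycardia, and continues "lacrimation, salivation, dysarthria, and diaphoresis/sweating have been reported during clinical trials with gepotidacin". The second is what increased cholinergic effects could lead to: "more severe symptoms including atrioventricular block, seizure/convulsions, bronchospasm, and vasovagal syncope". For the second group the protocol adds that no causal link to gepotidacin has been established.

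SAP 8.2.3 turns this into a rule: a reported event in the 12.4.3 table, starting no later than 12 hours after the last dose, "will be included in the programmatic identification of AChE-I related AESI". Cardiovascular AESIs (SAP 8.2.2) are likewise defined by match to a preferred-term list in 12.4.3. Gastrointestinal AESIs are defined by system organ class.

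Protocol 10.4.3 says AESIs will be assessed by both manual and programmatic review, as described in the analysis plan. SAP 8.2 describes the programmatic part only, while SAP 2.1 reports no change from the protocol's planned analyses.

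**The concern.** The AChE-I list should put into operation the effects set out in Protocol 3.3.1. If a named effect is missing, the rule gives it no weight however often it occurs. The list feeds:

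- the AChE-I tables (3.107 and 3.118 to 3.122), including the onset, duration and lag summaries;
- the cumulative-grade bar charts (Figures 3.103 and 3.104);
- the relative-risk plot (Figure 3.106);
- the AChE-I line of the benefit-risk plot (Figure 3.301).

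AESI status also matters in SAP 8.5.2, where AESIs go straight onto the short list of potential adverse reactions and most other events must first pass a numerical screen. A manual review could repair an incomplete list, but the SAP gives no procedure for one.

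**Working it through.** **Step 1. Compare the named effects with the lists.** Both lists in SAP 12.4.3 were searched for each event that Protocol 3.3.1 names under AChE inhibition. The AChE-I list has 73 entries, 72 of them distinct (Bradycardia is printed twice). The cardiovascular list has 165.

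| Event named in Protocol 3.3.1 | On the AChE-I list? | If not, on the cardiovascular list? |
|---|---|---|
| Diarrhea, nausea, vomiting, GI cramping and pain | Yes | |
| Dyspnea, bradycardia | Yes | |
| Lacrimation, salivation, sweating | Yes | |
| Seizure/convulsions, bronchospasm | Yes | |
| Vasovagal syncope | Yes, as Syncope | |
| **Dysarthria** | **No** (no speech term either) | **No** |
| **AV block** | **No** (no term containing block) | Yes: unspecified, paroxysmal, first degree, second degree, complete |

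Dysarthria is the only unmatched event in the first group, and AV block the only one in the second. The caveat about causality cannot explain the AV-block gap, because it applies equally to the three severe effects that are listed.

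**Step 2. Rule out a lost row.** Both columns of the AChE-I list are in strict alphabetical order. The one blank cell lies between Syncope and Tonic clonic movements, and the repeated Bradycardia lies between Autonomic seizure and Bronchial hyperreactivity. Neither slot could hold Dysarthria (due before Dyspnoea) or Atrioventricular block (due between Atonic seizures and Atypical benign partial epilepsy).

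**Step 3. Effect on the cumulative grade.** SAP 8.2.3 sums the grades and bands the total: 0 is grade 0, 1 to 3 is grade 1, 4 to 6 is grade 2. Take a hypothetical gepotidacin participant with Grade 2 nausea, Grade 1 diarrhoea and Grade 1 dysarthria, all in the window:

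- under the SAP list: 2 + 1 = 3, cumulative grade 1;
- with dysarthria listed: 2 + 1 + 1 = 4, cumulative grade 2;
- non-GI score: 0 (grade 0) under the SAP list, 1 (grade 1) with dysarthria listed.

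**Step 4. Effect on the short list.** If the comparator arm has no events, a non-AESI term needs at least 3 gepotidacin participants (SAP 8.5.2). The documents give no rate for dysarthria, so the SAP's illustrative rate is used first, with n = 310 and X ~ Binomial(n, p).

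- p = 0.75%: P(X=0) = 0.9925^310 = 0.097, so P(X≥1) = 0.903, which reproduces the SAP's 90%. P(X=1) = 310 × 0.0075 × 0.9925^309 = 0.227. P(X=2) = 47,895 × 0.0075² × 0.9925^308 = 0.265. Hence P(X≥3) = 1 − 0.097 − 0.227 − 0.265 = 0.411.
- p = 0.5% (assumed): the same formulas give P(X≥1) = 0.79 and P(X≥3) = 0.20.

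One or two cases would then occur with probability 0.903 − 0.411 = 0.49, or 0.79 − 0.20 = 0.59. In that situation AESI status would secure a place on the short list and the numerical screen would not. This applies to events that are neither serious nor severe, with no comparator events and nothing else in the same high-level term.

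**The case against.** The strongest reply is that no safety data are lost. Every treatment-emergent event is tabulated by preferred term, all high-level terms are screened for relative risk, and serious and severe events go directly to qualitative review. This stands, and it limits the point to AESI classification in descriptive displays.

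It can also be said that the manual review remains in force, because SAP 2.1 declares no change. But Protocol 10.4.3 leaves its description to the analysis plan, which has none, so nobody can tell whether it would add a term to the AESI counts.

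The text extraction might be at fault. One entry just before Dyspnoea, Drizzling, is not an obvious clinical term and may be a misreading. It looks closer to drooling than to dysarthria, but the source list should be checked.

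Four stronger readings are tempting, and the documents do not support them:

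- **AV block is lost as an AESI.** It is not: five AV-block terms are on the cardiovascular list. Sinus bradycardia is there too, and Bradycardia and Heart rate decreased are on the AChE-I list.
- **QT prolongation cannot be counted as a cardiovascular AESI.** Protocol 3.3.1 does say that "gepotidacin may cause mild, reversible heart rate effects and QT prolongation". But the cardiovascular list follows the event categories in Protocol Appendix 4 and contains Long QT syndrome, Long QT syndrome congenital and Torsade de pointes. Only a term for QT prolongation as an ECG finding is absent, so capture depends on coding, which the documents do not give. SAP 8.5.2 also says of QT prolongation "It is a very rare serious event that has been observed in early phase gepotidacin studies" and short-lists it automatically through HLT ECG investigations, though that output is reported outside the study report. An ECG is required only at Baseline.
- **The AESI relative risks are biased toward no difference.** No event rates are given. The forest plot is drawn event by event, so an omitted term leaves the others unchanged. For QT, Protocol 3.3.1 says azithromycin carries the risk too.
- **The sponsor already attributes these events to gepotidacin.** The protocol calls dysarthria possibly consistent with AChE inhibition, and for AV block says no causal relationship is established.

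**Conclusion.** The concern holds for the AChE-I list. Under the SAP's rule dysarthria cannot be an AESI of any kind, assuming it is not coded to the gastrointestinal system organ class (the documents give no coding). It also loses automatic short-listing. AV block is missing only from the AChE-I tables, cumulative grade, timing summaries and relative-risk displays. The manual review that could correct this is promised in the protocol and left undescribed in the SAP.

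The size cannot be stated as a number of events. The grade example shows that one omitted Grade 1 event can move a participant up a band. The short-list probabilities hold only at the assumed rates and under the conditions given with them. The primary efficacy analysis and overall AE reporting are unaffected. The absent ECG-finding term for QT prolongation is a minor point. Nothing is concluded about the direction of any bias or the share of QT events missed.

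**What to change.** Before unblinding:

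1. In SAP 12.4.3, add Dysarthria and the five AV-block terms already on the cardiovascular list to the AChE-I list. Sinus bradycardia may be added for consistency with Bradycardia. If any named effect is left out on purpose, give the reason.
2. In SAP 8.2, write in the manual review from Protocol 10.4.3: who reviews which terms, blinded to treatment, and how a term found this way enters the AESI counts.
3. As a minor item, add a term for QT prolongation as an ECG finding to the cardiovascular list, or state that such events are handled only through SAP 8.5.2.

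The cost is a few lines in a programming list and a short paragraph in the SAP. No new data are needed. AChE-I AESI counts may rise slightly, and AV block would appear under both the AChE-I and cardiovascular headings, which a table footnote should say.
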